## Study Flowchart

**Table 1 Flow chart of dose escalation in Part A**

	Screening period	Single dose / Cycle 0			Cycle 1				Cycle 2	Cycle 3 and thereafter	End of treatment/withdrawal	28-day follow-up	Disease progression
Follow-up visit	1	1.1	1.2	1.3	2	3	4	5	6	7 and thereafter			
Day	-28~0	C0D1	C0D2	C0D3	C1D1	C1D8	C1D15	C1D21	C2D1	D1			
Visit window (day)	NA	0	0	0	0	0	0	0	0	±3	±3	±3	
Informed Consent Form	X												
Demographic data 	X												
Tumor history / other medical history 	X												
Inclusion / exclusion criteria	X												
Screen for infectious diseases 	X												
ECOG 	X	X			X				X	X	X		
EGFR testing 	X												
Physical examination 	X	X			X	X	X	X		X	X		
Vital signs 	X	X	X		X	X	X	X	X	X	X		
Height 	X												
Body weight 	X	X			X				X	X	X		
Clinical laboratory tests (hematology, blood biochemistry and urinalysis) 	X				X	X	X	X		X	X		

ECG 	X	X	X		X	X	X	X		X	X		
Pregnancy test (only for women of childbearing age) 	X										X		
Nervous system examination 	X	X							X	X (D1 of each cycle until PD)			
Ophthalmology examination 	X										X		
CSF collection for cytological test and biochemical test (only for LM patients) 	X								X	X			
CSF collection for assessment of drug exposure 									X				
Imaging evaluation 	X								X	X (relative to C1D1, every 6 weeks up to PD)			
QLQ C-30 	X								X	X (relative to C1D1, every 6 weeks up to end of treatment)			
QLQ BN-20 	X								X	X (relative to C1D1, every 6 weeks up to PD)			
Administration of AZD3759 		X			<————→								
Subject's diary card 					<————→								
PK sampling 		X	X	X	X	X	X	X					
Concomitant medications 	<												
Adverse events 	<												

1. Demographics, including gender, date of birth, nationality, smoking history, height and body weight.
2. Tumor history and other medical history will be recorded separately. Other medical history includes all active diseases, and any diseases diagnosed in the past 10 years that the investigator considers clinically significant. Tumor history includes all previous tumors other than that evaluated in this study, even the diagnosis was made more than 10 years prior to screening visit.

3. Screen for infectious diseases include HIV antibody, two pairs of semi-hepatitis B (quantification of HBV-DNA may be performed if required) and HCV antibody (HCV RNA is required if HCV antibody is positive).
4. ECOG score will be obtained at screening period, on C0D1, C1D1 and Day 1 of every cycle until end of treatment/withdrawal.
5. At screening period, EGFR mutation in blood or tumor tissue should be determined in a qualified laboratory, and T790M mutation status will also be determined.
6. Physical examination includes: general appearance, skin, head and neck (including ears, eyes, nose and throat), respiratory, cardiovascular, abdomen, lymph nodes, thyroid gland and musculoskeletal system (including spine and limbs). Physical examination will be performed at Screening period, and on C0D1, C1D1, C1D8, C1D15, C1D21 and on Day 1 of cycle 3 and each cycle afterwards until the end of treatment.
7. Vital signs include blood pressure, pulse and body temperature, and will be monitored at screening period, pre-dose and 2h, 6h and 24h post-dose at C0D1, pre-dose at C1D1, C1D8 and C1D15, pre-dose and 2h and 6h post-dose at C1D21, pre-dose at C2D1 and pre-dose on day 1 of Cycle 3 and each cycle starts afterwards. Moreover, additional vital signs may be determined as needed in case of any cardiac adverse event, and vital signs should be performed at withdrawal of study treatment. A time window of 30 minutes is permitted for vital signs.
8. Height will be measured only at screening period. Body weight will be measured at screening period, on Day 1 of every cycle and at withdrawal of study treatment.
9. Blood and urine samples for clinical laboratory tests will be collected from subjects at screening period, pre-dose on C1D1, C1D8, C1D15, C1D21 and pre dose on Day 1 of cycle 3 and each cycle afterwards and at withdrawal of study treatment. The clinical laboratory tests of screening should be performed within 7 days prior to the initiation of treatment.
10. ECG should be obtained in supine position after adequate rest. A time window of 1 hour is permitted. At screening period, pre-dose and 2h, 6h and 24h post-dose on C0D1, pre-dose on C1D1, C1D8 and C1D15, pre-dose and 2h and 6h post-dose on C1D21, and on Day 1 during follow-up of each cycle from cycle 3. Moreover, additional ECG may be obtained as needed in case of any cardiac adverse event. If QTcF  $\geq$  CTC AE 3, repeat ECG measurements for consecutive 3 times immediately and take the average. ECG should be obtained at withdrawal of study treatment.
11. For non-surgical sterilized women of child-bearing potential, blood sample for pregnancy test shall be collected at screening and withdrawal of study treatment. Menopause is defined as permanent cessation of menorrhea. Women are considered post-menopausal if they (usually older than 45 years) have had 12 months of natural (spontaneous) amenorrhea.
12. Neurological examination will be performed at screening period and on C0D1 and Day 1 of every cycle from Cycle 2 until disease progression or death (death not due to disease progression) or initiation of another anti-tumor treatment. For patients who discontinue the study treatment due to reasons other than disease progression, neurological examination after treatment discontinuation should be performed at follow-up tumor radiographic assessment. Neurological examination should be recorded on a separate "Neurological Function Examination" Case Report Form.
13. Ophthalmological examination should be performed at screening period and withdrawal of study treatment, or in case of any visual symptom (including blurred vision).

14. For LM patients with implanted Ommaya reservoir, CSF samples will be collected at screening and every 6 weeks ± 1 week (relative to C1D1) until disease progression or death (death not due to disease progression) or initiation of another anti-tumor treatment. For LM patients without implanted Ommaya reservoir, CSF samples will be collected at least at screening and Week 12. For LM patients in single-center dose escalation in Part A who participate in plasma PK assessment, 0.5 mL CSF will be collected for assessment of drug exposure pre-dose on Day 1 Cycle 2 (C2D1) in addition to CSF collection for cytological test and biochemical test. 10 ml CSF shall be collected each time. CSF responders should be confirmed through repeated test at least 4 weeks after initial negative conversion.
15. For subjects who participate in Part A plasma PK assessment, 0.5 mL CSF will be collected for assessment of drug exposure pre-dose on C2D1.
16. Radiographic assessment performed within 28 days before initiation of study treatment can be used as the baseline assessment, radiographic assessment will be performed on C2D1, and subsequent radiographic assessments will be performed every 6 weeks ± 1 week (relative to C1D1) until disease progression or death (death not due to disease progression) or initiation of another anti-tumor treatment, regardless of withdrawal from AZD3759 treatment. For patients who withdraws from the study due to reasons other than disease progression, if time to the last scheduled assessment from withdrawal from the study is more than 4 weeks, additional radiographic assessment should be performed at study withdrawal.
17. Questionnaire will be completed at screening period, on C2D1 and every 6 weeks ± 1 week (relative to C1D1) thereafter. QLQ C-30 has to be collected until the withdrawal of study treatment, and QLQ BN-20 has to be collected until disease progression or death (death not due to disease progression) or initiation of another anti-tumor treatment. For patients who withdraws from the study due to reasons other than disease progression, if time to the last scheduled assessment from withdrawal from the study is more than 4 weeks, QLQ BN-20 questionnaire should be completed at study withdrawal. Patients must complete the questionnaire before visit study procedures and communication with the doctor about disease condition. Patients will have to complete the questionnaire independently.
18. The first dose should be taken at C0D1 and then commence twice daily dosing at C1D1 in fasting state. Each patient should take the drug at fixed time points during study treatment as far as possible. Dosing interval is 12 hours. Patients should not eat in 2 h post-dose nor drink in 1h post-dose. Administration in the hospital will be supervised by a doctor or nurse, and administered dose and time will be recorded on eCRF. For self-administration at home, time of administration and administered dose every day should be recorded on subject's diary card.
19. Venous blood samples (3 mL each time) for PK evaluation will be collected at pre-dose and 0.5h, 1h, 1.5h, 2h, 3h, 4h, 6h, 8h, 10h, 12h, 24h (C0D2) and 48h (C0D3) after the first dose (C0D1). Blood samples for PK evaluation will be collected during multiple dosing at pre-dose of C1D15, C1D21 and C2D1 and 0.5h, 1h, 1.5h, 2h, 3h, 4h, 6h, 8h, 10h, 12h post dose on C1D21.
20. Concomitant medications and treatments received within 28 days prior to screening and during study treatment will be recorded through completion of 28-day follow-up after the end of study treatment.
21. Adverse events will be recorded from signing informed consent form through 28-day follow-up after the end of study treatment, and will be followed up till adverse event is resolved or stable.

**Table 2 Flow chart of dose expansion in Part A**

	Screening period	Single dose / Cycle 0			Cycle 1				Cycle 2	Cycle 3 and thereafter	End of treatment/withdrawal	28-day follow-up	Disease progression
Follow-up visit	1	1.1	1.2	1.3	2	3	4	5	6	7 and thereafter			
Day	-28~0	C0D1	C0D2	C0D3	C1D1	C1D8	C1D15	C1D21	C2D1	D1			
Visit window (days)	NA	0	0	0	0	0	0	0	0	±3	±3	±3	
Informed Consent Form	X												
Demographic data 	X												
Tumor history/other medical history 	X												
Inclusion/exclusion criteria	X												
Screen for infectious diseases 	X												
ECOG 	X	X			X				X	X	X		
EGFR testing 	X												
Physical examination 	X	X			X	X	X	X		X	X		
Vital signs 	X	X	X		X	X	X	X	X	X	X		
Height 	X												
Body weight 	X	X			X				X	X	X		
Clinical laboratory tests (hematology, blood biochemistry and urinalysis) 	X				X	X	X	X		X	X		
ECG 	X	X	X		X	X	X	X		X	X		
Pregnancy test (only for women of childbearing age) 	X										X		

Nervous system examination 	X	X						X	X (D1 of each cycle until PD)			
Ophthalmology examination 	X									X		
CSF collection for cytological test and biochemical test (only for LM patients) 	X								X			
Imaging evaluation 	X								X (relative to C1D1, every 6 weeks up to PD)			
QLQ C-30 	X							X	X (relative to C1D1, every 6 weeks up to end of treatment)			
QLQ BN-20 	X							X	X (relative to C1D1, every 6 weeks up to PD)			
Administration of AZD3759 		X		<								
Subject's diary card 				<								
PK sampling 		X	X	X	X	X	X	X				
Concomitant medications 	<											
Adverse events 	<											

1. Demographics, including gender, date of birth, nationality, smoking history, height and body weight.
2. Tumor history and other medical history will be recorded separately. Other medical history includes all active diseases, and any diseases diagnosed in the past 10 years that the investigator considers clinically significant. Tumor history includes all previous tumors other than that evaluated in this study, even the diagnosis was made more than 10 years prior to screening visit.
3. Screen for infectious diseases include HIV antibody, two pairs of semi-hepatitis B (quantification of HBV-DNA may be performed if required) and HCV antibody (HCV RNA is required if HCV antibody is positive).
4. ECOG score will be obtained at Screening period, on C0D1, C1D1 and Day 1 of every cycle until end of treatment/withdrawal.
5. At screening period, EGFR mutation in blood or tumor tissue should be determined in a qualified laboratory, and T790M mutation status will also be determined.

6. Physical examination includes: general appearance, skin, head and neck (including ears, eyes, nose and throat), respiratory, cardiovascular, abdomen, lymph nodes, thyroid gland and musculoskeletal system (including spine and limbs). Physical examination will be performed at screening period, and on C0D1, C1D1, C1D8, C1D15, C1D21 and on Day 1 of cycle 3 and each cycle afterwards until the end of treatment.
7. Vital signs include blood pressure, pulse and body temperature, and will be monitored at screening period, pre-dose and 2h, 6h, and 24h post-dose at C0D1, pre-dose at C1D1, C1D8 and C1D15, pre-dose and 2h and 6h post-dose at C1D21, and pre-dose on Day 1 of every cycle from Cycle 2. Moreover, additional vital signs may be determined as needed in case of any cardiac adverse event, and vital signs should be performed at withdrawal of study treatment. A time window of 30 minutes is permitted for vital signs.
8. Height will be measured only at screening period. Body weight will be measured at screening period, on Day 1 of every cycle and at withdrawal of study treatment.
9. Blood and urine samples for clinical laboratory tests will be collected from subjects at screening period, pre-dose on C1D1, C1D8, C1D15, C1D21 and pre dose on Day 1 of cycle 3 and each cycle afterwards and at withdrawal of study treatment. The clinical laboratory tests of screening should be performed within 7 days prior to the initiation of treatment.
10. ECG should be obtained in supine position after adequate rest. A time window of 1 hour is permitted. At screening period, pre-dose and 2h, 6h and 24h post-dose on C0D1, pre-dose on C1D1, C1D8 and C1D15, pre-dose and 2h and 6h post-dose on C1D21, and on Day 1 during follow-up of each cycle from cycle 3. Moreover, additional ECG may be obtained as needed in case of any cardiac adverse event. If QTcF  $\geq$  CTC AE 3, repeat ECG measurements for consecutive 3 times immediately and take the average. ECG should be obtained at withdrawal of study treatment.
11. For non-surgical sterilized women of child-bearing potential, blood sample for pregnancy test should be collected at screening and withdrawal of study treatment. Menopause is defined as permanent cession of menorrhea. Women are considered post-menopausal if they (usually older than 45 years) have had 12 months of natural (spontaneous) amenorrhea.
12. Neurological examination will be performed at screening period and on C0D1 and Day 1 of every cycle from Cycle 2 until disease progression or death (death not due to disease progression) or initiation of another anti-tumor treatment. For patients who discontinue the study treatment due to reasons other than disease progression, neurological examination after treatment discontinuation should be performed at follow-up tumor radiographic assessment. Neurological examination should be recorded on a separate "Neurological Function Examination" Case Report Form.
13. Ophthalmological examination should be performed at screening period and withdrawal of study treatment, or in case of any visual symptom (including blurred vision).
14. For LM patients with implanted Ommaya reservoir, CSF samples will be collected at screening and every 6 weeks  $\pm$  1 week (relative to C1D1) until disease progression or death (death not due to disease progression) or initiation of another anti-tumor treatment. For LM patients without implanted Ommaya reservoir, CSF samples will be collected at least at screening and Week 12. 10 ml CSF shall be collected each time.. CSF responders should be confirmed through repeated test at least 4 weeks after initial negative conversion.

15. Radiographic assessment performed within 28 days before initiation of study treatment can be used as the baseline assessment, and subsequent radiographic assessments will be performed every 6 weeks  $\pm$  1 week (relative to C1D1) until disease progression or death (death not due to disease progression) or initiation of another anti-tumor treatment, regardless of withdrawal from AZD3759 treatment. For patients who withdraws from the study due to reasons other than disease progression, if time to the last assessment from the withdrawal from study is more than 4 weeks, additional radiographic assessment should be performed at study withdrawal.
16. Questionnaire will be completed at screening period, on C2D1 and every 6 weeks  $\pm$  1 week (relative to C1D1) thereafter. QLQ C-30 has to be collected until the withdrawal of study treatment, and QLQ BN-20 has to be collected until disease progression or death (death not due to disease progression) or initiation of another anti-tumor treatment. For patients who withdraws from the study due to reasons other than disease progression, if time to the last assessment from the withdrawal from study is more than 4 weeks, QLQ BN-20 questionnaire should be completed at study withdrawal. Patients must complete the questionnaire before visit study procedures and communication with the doctor about disease condition. Patients will have to complete the questionnaire independently.
17. The first dose should be taken at C0D1 and then commence twice daily dosing at C1D1 in fasting state. Each patient should take the drug at fixed time points during study treatment as far as possible. Dosing interval is 12 hours. Patients should not eat in 2 h post-dose nor drink in 1h post-dose. Administration in the hospital will be supervised by a doctor or nurse, and administered dose and time will be recorded on eCRF. For self-administration at home, time of administration and administered dose every day should be recorded on subject's diary card.
18. Venous blood samples (3 mL each time) for PK evaluation will be collected at pre-dose and 0.5h, 1h, 1.5h, 2h, 3h, 4h, 6h, 8h, 10h, 12h, 24h (C0D2) and 48h (C0D3) after the first dose (C0D1). Blood samples for PK evaluation will be collected during multiple dosing at pre-dose of C1D15, C1D21 and C2D1 and 0.5h, 1h, 1.5h, 2h, 3h, 4h, 6h, 8h, 10h, 12h post dose on C1D21.
19. Concomitant medications and treatments received within 28 days prior to screening and during study treatment will be recorded through 28-day follow-up after the end of study treatment.
20. Adverse events will be recorded from signing informed consent form through 28-day follow-up after the end of study treatment, and will be followed up till adverse event is resolved or stable.

**Table 3 Flow chart of Phase II study in Part B**

	Screening period	Cycle 1	Cycle 2 and thereafter	End of treatment/withdrawal	28-day follow-up	Disease progression	Survival follow-up
Follow-up visit	1	2	3 and thereafter				
Day	-28~0	C1D1	D1				
Visit window (days)	NA	0	±3	±3	±3		±7
Informed Consent Form	X						
Demographic data 	X						
Tumor history/other medical history 	X						
Inclusion/exclusion criteria	X						
Screen for infectious diseases 	X						
ECOG score 	X	X	X	X			
EGFR testing 	X						
Physical examination 	X	X	X	X			
Vital signs 	X	X	X	X			
Height 	X						
Body weight 	X		X	X			
Clinical laboratory tests (hematology, blood biochemistry and urinalysis) 	X	X	X	X			
ECG 	X	X	X	X			
Pregnancy test (only for women of childbearing age) 	X			X			
Nervous system examination 	X	X	X	X (D1 of each cycle until progression)			
Ophthalmology examination 	X			X			

CSF collection for cytological test and biochemical test (only for patients with metastases to meninges) 	X	X				
Oncologic imaging evaluation 	X		X(relative to C1D1, every 6 weeks up to progression)			
QLQ C-30 	X		X(relative to C1D1, every 6 weeks)	X		
QLQ BN-20 	X		X(relative to C1D1, every 6 weeks up to progression)			
Administration of AZD3759 			<—————→			
Subject's diary card 			<—————→			
Concomitant medications 			<—————→			
Adverse events 			<—————→			
Survival follow-up 						X (every 6 weeks)

1. Demographics, including gender, date of birth, nationality, smoking history, height and body weight.
2. Tumor history and other medical history will be recorded separately. Other medical history includes all active diseases, and any diseases diagnosed in the past 10 years that the investigator considers clinically significant. Tumor history includes all previous tumors other than that evaluated in this study, even the diagnosis was made more than 10 years prior to screening visit.
3. Screen for infectious diseases include HIV antibody, two pairs of semi-hepatitis B (quantification of HBV-DNA may be performed if required) and HCV antibody (HCV RNA is required if HCV antibody is positive).
4. ECOG score will be obtained at Screening period, on C1D1 and Day 1 of every cycle until end of treatment/withdrawal.
5. At screening period, EGFR mutation in blood or tumor tissue should be determined in a qualified laboratory, and T790M mutation status will also be determined.
6. Physical examination includes: general appearance, skin, head and neck (including ears, eyes, nose and throat), respiratory, cardiovascular, abdomen, lymph nodes, thyroid gland and musculoskeletal system (including spine and limbs). Physical examination will be performed at screening period, and on C1D1 and Day 1 of every cycle until end of treatment.

7. Vital signs include blood pressure, pulse and body temperature, and will be monitored at screening period, pre-dose on C1D1, and pre-dose on Day 1 of every cycle from Cycle 2. Moreover, additional vital signs may be performed as needed in case of any cardiac adverse event, and vital signs should be performed at withdrawal of study treatment.
8. Height will be measured only at screening period. Body weight will be measured at screening period, on Day 1 of every cycle and at withdrawal of study treatment.
9. Blood and urine samples for clinical laboratory tests will be collected from subjects at screening period, pre-dose on C1D1 and Day 1 of every cycle from Cycle 2, and at withdrawal of study treatment.
10. ECG should be obtained in supine position after adequate rest. At screening period, pre-dose and post-dose on C1D1, and post-dose on Day 1 of every cycle from Cycle 2 for the day of dosing. Moreover, additional ECG may be obtained as needed in case of any cardiac adverse event. If QTcF  $\geq$  CTC AE 3, repeat ECG measurements for consecutive 3 times immediately and take the average. ECG should be obtained at withdrawal of study treatment.
11. For non-surgical sterilized women of child-bearing potential, blood sample for pregnancy test should be collected at screening and withdrawal of study treatment. Menopause is defined as permanent cessation of menstruation. Women are considered post-menopausal if they (usually older than 45 years) have had 12 months of natural (spontaneous) amenorrhea.
12. Neurological examination will be performed at screening period and on Day 1 of every cycle until disease progression or death (death not due to disease progression) or initiation of another anti-tumor treatment. For patients who discontinue the study treatment due to reasons other than disease progression, neurological examination after treatment discontinuation should be performed at follow-up tumor radiographic assessment. Neurological examination should be recorded on a separate "Neurological Function Examination" Case Report Form.
13. Ophthalmological examination should be performed at screening period and withdrawal of study treatment, or in case of any visual symptom (including blurred vision).
14. For LM patients with implanted Ommaya reservoir, CSF samples will be collected at screening and every 6 weeks  $\pm$  1 week (relative to C1D1) until disease progression. For LM patients without implanted Ommaya reservoir, CSF samples will be collected at least at screening and Week 12. 10 ml CSF shall be collected each time. CSF responders should be confirmed through repeated test at least 4 weeks after initial negative conversion.
15. Radiographic assessment performed within 28 days before initiation of study treatment can be used as the baseline assessment, and subsequent radiographic assessments will be performed every 6 weeks  $\pm$  1 week (relative to C1D1) until disease progression or death (death not due to disease progression) or initiation of another anti-tumor treatment, regardless of withdrawal from AZD3759 treatment. For patients who withdraw from the study due to reasons other than disease progression, if time to the last assessment from the withdrawal from study is more than 4 weeks, additional radiographic assessment should be performed at study withdrawal.
16. Questionnaire will be completed at screening period and every 6 weeks  $\pm$  1 week (relative to C1D1). QLQ C-30 has to be collected until the withdrawal of study treatment, and QLQ BN-20 has to be collected until disease progression or death (death not due to disease progression) or

initiation of another anti-tumor treatment. For patients who withdraws from the study due to reasons other than disease progression, if time to the last scheduled assessment from withdrawal from the study is more than 4 weeks, QLQ BN-20 questionnaire should be completed at study withdrawal. Patients must complete the questionnaire before visit study procedures and communication with the doctor about disease condition. Patients will have to complete the questionnaire independently.

17. Administration will be twice daily in fasting state. Each patient should take the drug at fixed time points during study treatment as far as possible. Dosing interval is 12 hours. Patients should not eat in 2 h post-dose nor drink in 1h post-dose. Administration in the hospital will be supervised by a doctor or nurse, and administered dose and time will be recorded on eCRF. For self-administration at home, time of administration and administered dose every day should be recorded on subject's diary card.
18. Concomitant medications and treatments received within 28 days prior to screening and during study treatment will be recorded through 28-day follow-up after the end of study treatment.
19. Adverse events will be recorded from signing informed consent form through 28-day follow-up after the end of study treatment, and will be followed up till adverse event is resolved or stable.
20. Once 28-day follow-up visit is completed, all patients in Phase II study period will be contacted by phone every 6 weeks for overall survival follow-up, until patient's death or loss to follow-up or withdrawal of informed consent. During this period, any other treatment for non-small cell lung cancer should be collected via eCRF.

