Main inclusion/exclusion criteria	
sampling days.
 
Inclusion criteria:
 
Patients must meet all of the following criteria to participate in the study:
 
 
1. Subjects must provide written informed consent before any study related procedure.
 
2. Male or female Chinese patients ≥18 years old.
 
3. Histologically or cytologically confirmed non-small cell lung cancer with activating mutation in EGFR gene (including Exon19Del and/or L858R). A validated and robust test method reviewed and approved by the regulatory authority should be used to determine EGFR mutation status in tissue or plasma locally.
 
4. Patients with advanced non-small cell lung cancer (stage IV) with documented BM and/or LM. Part A dose escalation can include EGFR TKI-naïve NSCLC patients with measurable lung lesion and no BM. Patients with BM and/or LM in each dose group shall account for at least one-third.
 
5. According to Eastern Cooperative Oncology Group (ECOG) Scale, performance status is grade 0 to 1, without worsening in the past 2 weeks, and life expectancy of at least 3 months. If ECOG performance status is grade 2 due to LM disease, the patient can also be enrolled.
 
6. Non-surgical sterilized women of child-bearing potential and male subjects shall agree to take medically acceptable contraception measures during dosing of investigational drug and 3 months after completion of study treatment. Non-surgical sterilized women of child-bearing potential must have negative blood pregnancy test at screening.
 
7. Asymptomatic BM patients who have not received prior treatment with any EGFR TKI or symptomatic BM patients who are not warranted temporally for definitive local treatment (surgery or radiotherapy). For patients with prior local treatment for BM lesion (surgery or radiotherapy), intracranial lesion progression is required.
 
8. BM patients must have at least one measurable intracranial lesion; in case of prior radiotherapy for BM lesion, progression is required and must meet measurable lesion
 

--	---

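### The only pre-treatment QLQ C-30 and QLQ BN-20 are at screening, up to 28 days before first dose, so symptom change before dosing may be counted as on-treatment change

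*Combined protocol and SAP*

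**What the plan says.** **Questionnaire schedule.** In Part B (Table 3, footnote 16): "Questionnaire will be completed at screening period and every 6 weeks", with a window of one week either side and time counted from C1D1. The C1D1 column of the chart is empty for both questionnaires. In Part A escalation (Table 1, footnote 17): "Questionnaire will be completed at screening period, on C2D1 and every 6 weeks ± 1 week". Part A expansion (Table 2, footnote 16) has the same schedule. Neither Part A chart has a questionnaire on C0D1 or C1D1. Screening in each chart is Day -28 to 0, and no footnote sets a narrower limit for the questionnaires.

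**Other assessments.** In Table 3 (footnotes 4 and 12), "ECOG score will be obtained at Screening period, on C1D1 and Day 1 of every cycle until end of treatment/withdrawal" and "Neurological examination will be performed at screening period and on Day 1 of every cycle until disease progression". In Tables 1 and 2 both are also done on C0D1, the day of the first dose. For Part A laboratory tests (footnote 9 of Tables 1 and 2), "The clinical laboratory tests of screening should be performed within 7 days prior to the initiation of treatment".

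**Role of the PROs.** The Synopsis lists them as secondary endpoints in Part A and in both Part B cohorts. Its section on patient-reported outcomes gives their purpose as assessing quality of life, symptoms and improvement in CNS symptoms. The synopsis and flow charts define no PRO baseline.

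**The concern.** Improvement has to be measured against a reference value, and the screening form is the only pre-treatment value the schedule provides. Follow-up forms are tied to C1D1, but the reference form is tied only to a four-week window. With no control arm described, there is no comparison group to separate change before the first dose from change after it.

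The eligibility criteria make such change plausible in both directions. Before first dose, the Synopsis excludes cytotoxic chemotherapy only within 14 days, small-area palliative radiotherapy only within 1 week, and a prior EGFR TKI within 8 days or 5 half-lives. Each of these can therefore end inside the 28-day window. A patient who fills in the form soon after such treatment and then recovers would appear to improve on AZD3759. Conversely, symptomatic BM patients and LM patients with ECOG 2 can enter. One who worsens between the form and the first dose would show less benefit than was obtained.

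At stake is the interpretation of a secondary endpoint. The response endpoints are not affected.

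**Working it through.** The plan states no figure to reproduce. The check is where the forms fall, and how much of the interval between reference form and first follow-up form can precede any drug.

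**Step 1: compare the assessments**

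| Assessment | Screening | First-dose day (C0D1 in Part A, C1D1 in Part B) |
|---|---|---|
| QLQ C-30, QLQ BN-20 | Yes, Day -28 to 0 | No |
| ECOG | Yes | Yes |
| Neurological examination | Yes | Yes |
| Laboratory tests, Part A | Yes, within 7 days before treatment | Not on C0D1; repeated on C1D1 |

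The investigator-rated measures of function and neurological status are renewed at first dose. The patient's own report is not.

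**Step 2: inputs**

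- Pre = days from screening form to first dose: 0 to 28, from the screening column. I also show 7 days (the Part A laboratory limit) and 14 days.
- Post, Part B = days from C1D1 to the first follow-up form: 42, or 35 to 49 with the window of one week.
- Post, Part A = days from C0D1 to C2D1: about 23. This assumes 2 days for the 48-hour washout plus 21 days of Cycle 1.

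**Step 3: formula**

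Share of the interval before any drug = pre / (pre + post).

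**Step 4: results**

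| Pre (days) | Part B, post 35 | Part B, post 42 | Part B, post 49 | Part A at C2D1, post about 23 |
|---|---|---|---|---|
| 28 | 28/63 = 44.4% | 28/70 = 40.0% | 28/77 = 36.4% | 28/51 = 54.9% |
| 14 | 14/49 = 28.6% | 14/56 = 25.0% | 14/63 = 22.2% | 14/37 = 37.8% |
| 7 | 7/42 = 16.7% | 7/49 = 14.3% | 7/56 = 12.5% | 7/30 = 23.3% |
| 0 | 0% | 0% | 0% | 0% |

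The longest interval (77 days) gives the smallest share for a Day -28 form, because the late follow-up adds only time on drug. A pre-dose form on the first-dose day puts every patient in the bottom row.

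These figures are proportions of calendar time. Turning them into a bias in questionnaire score would need the rate of symptom change before dosing, which the documents do not give.

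**The case against.** **The plan limits pre-dose drift and lets some of it be seen.** Inclusion criterion 5 requires performance status not to have worsened in the past two weeks. Exclusion criteria 5 and 20 remove patients with the most unstable CNS disease. ECOG and the neurological examination, done at screening and at first dose, would show some drift. This stands as mitigation. It narrows the room for worsening but does not address recovery from earlier treatment, and neither examination is the patient's own report.

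**The same 28-day window is accepted for baseline imaging.** True, and a screening PRO baseline is consistent with it. But repeating a scan is a real burden, while repeating two questionnaires at a visit already attended is not.

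**No change-from-baseline PRO analysis is visible.** Also true. The text reviewed is the synopsis and flow charts, so a definition elsewhere cannot be ruled out. Such a definition could not, however, supply a first-dose form that the schedule does not collect.

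**A stronger reading that fails.** Footnote 16 of Table 3 says "Patients must complete the questionnaire before visit study procedures and communication with the doctor about disease condition", and inclusion criterion 1 says "Subjects must provide written informed consent before any study related procedure". A reader might infer that the screening form cannot satisfy the completion rule, and hence that baseline and follow-up are necessarily collected under different conditions. The documents do not support either step. The completion rule is worded per visit, screening can span several days, and nothing requires the form on the day of consent. A form given on a later screening day, before that day's procedures and doctor contact, complies. Nor does following consent set the screening form apart, since every form in the trial does so. What remains is that the plan does not say how the rule applies within the screening period.

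**Conclusion.** The point holds as a minor design improvement. The schedule allows a PRO reference value up to 28 days old at first dose and collects nothing later before treatment. Any symptom change in that gap may be counted as on-treatment change.

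In the extreme case of a Day -28 form, 36% to 44% of the interval to the first Part B follow-up form precedes any drug, and about 55% of the interval to C2D1 in Part A. Patients screened close to dosing would have little or no such gap. It would be wrong to read these percentages as the part of a score change that is not due to the drug.

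The conclusion rests on three assumptions: that the screening form serves as the reference for improvement, being the only one scheduled; that no concurrent control exists, as none is described; and, for the Part A figure only, that C0D1 to C2D1 takes about 23 days. Mixing of pre-dose and on-treatment change is possible for any patient with a gap, but neither its size nor its direction can be derived from the documents.

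**What to change.** 1. Add QLQ C-30 and QLQ BN-20 pre-dose on C0D1 in Tables 1 and 2 and pre-dose on C1D1 in Table 3, completed on arrival before that visit's procedures and any talk with the doctor about the disease.
2. Define this form as the PRO baseline. Use the screening form only when the first-dose form is missing, and report how many patients rely on it and the days from that form to first dose.
3. State in the questionnaire footnotes how the completion rule applies to a form given during screening.

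The cost is two short questionnaires once per patient, at a visit already attended, plus a line in each flow chart and its footnote. The screening form has to stay if it is to serve as the fallback, so its burden is not saved. A first-dose form that was not collected cannot be recovered at analysis.

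If the extra form is not acceptable, limiting the screening questionnaire to 7 days before first dose, as Part A does for laboratory tests, would cap the share at 12.5% to 16.7% in Part B and about 23% in Part A. That reduces the gap without closing it.
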